7.3 Potential Risks and Benefits of the Investigational Device

Risks and Benefits are detailed below. Loss of confidentiality is a potential risk; however, data are handled to minimize this risk. Hypoglycemia, hyperglycemia and ketone formation are always a risk in participants with T1D and participants will be monitored for this. As subjects will be pregnant, there are also potential unknown risks to the mother or fetus. Since no new medications are being used, and subjects are already actively managing their type 1 diabetes during their pregnancy, we believe any additional risk from using the study devices is minimal.

7.3.1 Known Potential Risks

7.3.1.1 Venipuncture Risks

A hollow needle/plastic tube will be placed in the arm for taking blood samples. Blood draws can cause some common reactions like pain, bruising, or redness at the sampling site. Less common reactions include bleeding from the sampling site, formation of a small blood clot or swelling of the vein and surrounding tissues, and fainting.

7.3.1.2 Fingerstick Risks

About 1 drop of blood will be removed by fingerstick for measuring blood glucose and sometimes Hemoglobin A1c (HbA1c) or other tests. This is a standard method used to obtain blood for routine hospital laboratory tests. Pain is common at the time of lancing. In about 1 in 10 cases, a small amount of bleeding under the skin will produce a bruise. A small scar may persist for several weeks. The risk of local infection is less than 1 in 1000. This should not be a significant contributor to risks in this study as fingersticks are part of the usual care for people with diabetes.

7.3.1.3 Subcutaneous Catheter Risks (CGM)

Participants using the CGM will be at low risk for developing a local skin infection at the site of the sensor needle placement. If a catheter is left under the skin for more than 24 hours, it is possible to get an infection where it goes into the skin, with swelling, redness and pain. There may be bleeding where the catheter is put in and bleeding under the skin causes a bruise (1 in 10 risk).

Study staff should verbally alert the participant that on rare occasions, the CGM may break and leave a small portion of the sensor probe under the skin that may cause redness, swelling or pain at the insertion site. The participant will be instructed to notify the study coordinator immediately if this occurs.

7.3.1.4 Risk of Hypoglycemia

As with any person having T1D and using insulin, there is always a risk of having a low blood sugar (hypoglycemia). The frequency of hypoglycemia should be no more and possibly less than it would be as part of daily living. Symptoms of hypoglycemia can include sweating, jitteriness, and not feeling well. Just as at home, there is the possibility of fainting or seizures (convulsions) and that for a few days the participant may not be as aware of symptoms of hypoglycemia. A CGM functioning poorly and significantly over-reading glucose values could lead to inappropriate insulin delivery. Fetal growth restriction or small for gestational neonates has been reported in pregnant women with excessive hypoglycemia using multiple daily injections or sensor augmented or standard insulin pump therapy.

7.3.1.5 Risk of Hyperglycemia

Hyperglycemia and ketonemia could occur if insulin delivery is attenuated or suspended for an extended period or if the pump or infusion set is not working properly. Stress can also induce hyperglycemia. A CGM functioning poorly and significantly under-reading glucose values could lead to inappropriate suspension of insulin delivery. In this study, subjects will take full insulin boluses for all their meals, whether or not they are using the closed-loop system. In addition, subjects will be medically supervised when undergoing stress assessments, with medical staff present who will increase insulin doses as needed if this proves necessary during the stress assessments. All subjects will be issued a ketone meter and ketone strips to use to carefully monitor for hyperglycemia and be given instructions on how to mitigate hyperglycemia should it occur. Chronic hyperglycemia can increase the risk of fetal macrosomia or large for gestational age neonate, polyhydramnios and neonatal hypoglycemia in the newborn fetus at the time of delivery. These are the same risks occur in pregnant women utilizing MDI or sensor augmented or standard insulin pump therapy. Acute hyperglycemia can lead to DKA that puts the fetus at

acute risk of acidosis and demise. Furthermore, DKA in pregnancy can occur at lower glucose levels than in the non-pregnant state, hence the need to be vigilant and intervene when the glucose level approaches 180 mg/dL

7.3.1.6 Risk of Device Reuse

The study CGM system is labeled for single use only. The sensor (the component of the system that enters the skin) will be single use only. The transmitter and receiver may be reused during the study after cleaning the device using a hospital-approved cleaning procedure. The transmitter is attached to the sensor but does not enter the skin and the receiver is a handheld device.

Participants will be informed that Food & Drug Administration (FDA) or relevant national authorities have approved these devices for single use and that by using them among multiple patients, bloodborne pathogens (i.e. Hepatitis B) may be spread through the use of multiple users.

The study insulin pump is labeled for single-patient use. During the study, this device may be reused after cleaning adhering to a hospital-approved cleaning procedure. All infusion set equipment will be single patient use only (infusion set insertion kits, tubing, cartridges etc.).

Participants will be informed that FDA or relevant national authorities typically approve the insulin pump device for single use and that by using them among multiple patients, bloodborne pathogens (i.e. Hepatitis B) may be spread through the use of multiple users.

The study phone may be reused after cleaning adhering to a hospital-approved cleaning procedure.

The study blood glucose meter and blood ketone meter are labeled for single-patient use. During the study, only one person can use each device as there are rare risks that bloodborne pathogens (i.e. Hepatitis B) may be spread through the use of multiple users.

7.3.1.7 Cleaning Procedure

All devices being reused in this study as noted above (i.e. the Tandem t:AP pump, the CGM receiver and transmitter, and the phone running the iAPS App) will be thoroughly cleaned prior to reuse. The person performing the cleaning will sanitize their hands and then put on gloves prior to cleaning.

CGM receivers/CGM Transmitters and/or Insulin pumps/Cellular Devices: Sanitize hands, and then put on gloves before opening 70% isopropyl alcohol pads. Thoroughly wipe the device with the alcohol pad. Then use 2 Clorox Healthcare®35309 Bleach Germicidal Wipes, one for pre-cleaning and one for disinfecting. After pre-cleaning wipe the device thoroughly and wet the exterior with a 2nd wipe. Allow the surface to stay wet for 3 minutes and then let air dry. Dispose of used pad and gloves. Equipment will be stored in a clean Ziploc bag.

Equipment will be allowed to dry completely. All cleaned equipment will be stored in a clean zipped bag until ready for reuse.

8 ADVERSE EVENTS, DEVICE ISSUES, AND STOPPING RULES

8.1 Adverse Events

8.1.1 Definitions

Adverse Event (AE): Any untoward medical occurrence in a study participant, irrespective of the relationship between the adverse event and the device(s) under investigation (see section 8.1.2 for reportable adverse events for this protocol).

Serious Adverse Event (SAE): Any untoward medical occurrence that:

- Results in death of the mother or the fetus.
- Is life-threatening; (a non-life-threatening event which, had it been more severe, might have become life-threatening, is not necessarily considered a serious adverse event).
- Requires inpatient hospitalization or prolongation of existing hospitalization.
- Results in persistent or significant disability/incapacity or substantial disruption of the ability to conduct normal life functions (sight threatening).
- Is a congenital anomaly or birth defect.
- Is considered a significant medical event by the investigator based on medical judgment (e.g., may jeopardize the participant or fetus or may require medical/surgical intervention to prevent one of the outcomes listed above).

Unanticipated Adverse Device Effect (UADE): Any serious adverse effect on health or safety or any life-threatening problem or death caused by, or associated with, a device, if that effect, problem, or death was not previously identified in nature, severity, or degree of incidence in the investigational plan or application (including a supplementary plan or application), or any other unanticipated serious problem associated with a device that relates to the rights, safety, or welfare of participants (21 CFR 812.3(s)).

Adverse Device Effect (ADE): Any untoward medical occurrence in a study participant which the device may have caused or to which the device may have contributed (Note that an Adverse Event Form is to be completed in addition to a Device Deficiency or Issue Form).

Device Complaints and Malfunctions: A device complication or complaint is something that happens to a device or related to device performance, whereas an adverse event happens to a participant. A device complaint may occur independently from an AE, or along with an AE. An AE may occur without a device complaint or there may be an AE related to a device complaint. A device malfunction is any failure of a device to meet its performance specifications or otherwise perform as intended. Performance specifications include all claims made in the labeling for the device. The intended performance of a device refers to the intended use for which the device is labeled or marketed. (21 CFR 803.3). Note: for reporting purposes, sites will not be asked to distinguish between device complaints and malfunctions.

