	Stewart et al, 2016	Stewart et al, 2018
Baseline HbA1c	6.8±0.6%	8.0±1.1%
Pre-eclampsia	31%	12.5%
Preterm	44%	NR
C-section	94%	81%
NICU admission	75%	69%
LGA	81%	44%
Congenital malformations	Not recorded	12.5%

Our consortium also is following a prospective cohort of 30 women who are participating in the Longitudinal Observation of Insulin Requirements and Sensor Use in Pregnancy (LOIS-P) study designed to track glycemic control and insulin pump setting changes throughout pregnancy. All subjects are enrolled before 17 weeks gestation, are using insulin pumps, are provided Dexcom G6 CGM, and are followed prospectively throughout their pregnancy and for 6 weeks post-partum. All subjects are contacted every 2 weeks. Data collected include CGM, insulin delivery, self-monitoring of blood glucose (SMBG), and maternal and fetal outcomes of pregnancy. Activity and diet logs are also being collected during 1 week in the 2nd and 3rd trimesters. This is a unique dataset that will pave the way for better understanding of the dynamic insulin requirements during pregnancy.

As of Jan 15, 2021, we have analyzed results from 25 subjects enrolled in the LOIS-P study referred to above. Only six participants achieved >70% recommended TIR for pregnancy. Between 18-24 and 26-30 weeks, mean daily percentage of CGM TIR was significantly lower, and time above range was significantly higher compared to the reference biweek. Time below target was unchanged. All primary outcomes were statistically significant ($p<0.003$). Daily basal insulin per kilogram was higher during weeks 6-10 and 28-40. Daily bolus and total insulin per kilogram were higher during weeks 22-40. Carbohydrate intake stayed stable. All insulin parameters were significantly increased from 22 weeks onwards. We conclude that insulin dosing changes significantly with advancing gestation and most participants did not achieve >70% TIR. This further illustrates the urgent unmet need for automated insulin delivery systems customized to this population's targets.

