- e. Subject's glycemic data will be reviewed and a documented contact will be completed at least weekly after the 72-hour check. If there is a significant deterioration of glycemic control as determined at any time or during the scheduled weekly contacts, leading to a significant worsening time in range compared to baseline (10% or more worsening of time in target range) and time in range consistently below 50%, the site clinical investigator will end the subject's participation in the study (Stopping criteria, section 8.4)
- f. After ~4 weeks, the study Data Safety and Monitoring Board (DSMB) will review a summary of the subject's glycemic data, to include any adverse events, to approve continued use of the system through the remainder of pregnancy if the subject desires. Success criteria based on CGM glycemic metrics, to be presented to the DSMB, before approval can be granted to move beyond three subjects, are the following:
 - a. CGM % Time ≤ 54 mg/dL = 2% or less
 - b. CGM % Time 63-140 mg/dL = greater than or equal to 50%
 - c. No Unanticipated Adverse Device Effects (UADE's)
- g. Follow up visit after delivery: Subjects will be called or seen in person before hospital discharge to ensure they have transitioned safely to their home devices. Maternal and neonatal outcomes will be recorded.

Subjects will be considered enrolled when, after completing the screening visit, the investigator has reviewed all enrollment criteria and signed off on the subject's enrollment. Up to 21 subjects may be enrolled.

In case of illness or cancellation, the visits may be rescheduled at the discretion of the investigator.

Study schedule and interventions are summarized in the table below:

Table . Schedule of Assessments Including Extension

	Screening	Open Loop Data Collection	Hybrid Closed-Loop Phase	End of Study Phone Call (Last study visit)	Extension Phase
Informed Consent	X				
Demographics	X				
Medical History	X				
Diabetes History	X				
Medication Use	X				
Vital Signs ¹	X		X		
Skin inspection (Sensor/Infusion Set Sites)	X				
Fetal Doptones			X		
Laboratory	X				
Point-of-care HbA1c	X				X ⁴
Insulin pump/CGM/glucometer data download	X		X		
CGM Training		X	X		
CGM Placement		X	X		
iAPS & Study Pump Closed-Loop Use			X	X	X
Fingersticks BG as required per protocol ²		X	X	X	X
CGM Calibrations ³		X	X	X	X
Competency assessment prior to discharge home with iAPS			X		
24, 48, and 72 hour contact, then a minimum of weekly contact with subjects.					X

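### Serious-event reporting does not expressly cover the live-born infant, and no end date is set for recording neonatal outcomes

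*Protocol*

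**What the plan says.** Protocol section 8.1.1 defines an adverse event as "Any untoward medical occurrence in a study participant, irrespective of the relationship between the adverse event and the device(s) under investigation". The list of serious criteria treats death and medical judgment by naming who is meant: death counts if it "Results in death of the mother or the fetus", and the judgment criterion's example is an event that "may jeopardize the participant or fetus". Other criteria name nobody, among them "Requires inpatient hospitalization or prolongation of existing hospitalization" and "Is a congenital anomaly or birth defect".

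Section 8.3 applies the 24-hour recording rule to SAEs and UADEs. Section 8.4.2 has the medical monitor informed of all SAEs and unanticipated device events. Section 8.5 gives the DSMB immediate notice of severe hypoglycemia, DKA, device-related SAEs and UADEs.

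After delivery there is one planned contact, in section 6.3, item 5(g): "Subjects will be called or seen in person before hospital discharge to ensure they have transitioned safely to their home devices". The next sentence says that maternal and neonatal outcomes are recorded. It gives no list, no end date and no route into adverse-event reporting.

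The protocol itself treats harm to the infant as a consequence of maternal glycemia. Section 2.2 lists neonatal hypoglycemia, intensive care admission and seizures. Section 7.3.1.5 names "polyhydramnios and neonatal hypoglycemia in the newborn fetus at the time of delivery" among the risks of chronic hyperglycemia. Table 4 reports "NICU admission" in the two cited closed-loop trials.

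**The concern.** The system is used through pregnancy, and part of the harm that the protocol fears would first be seen in the infant, after birth. Where the serious criteria do say whose death or jeopardy counts, they stop at the fetus.

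Two things are at stake. The first is consistency: with 21 women at three sites, one investigator may file a NICU stay as a hospitalization while another treats it as an outcome for the delivery form. A count of neonatal SAEs would then partly reflect reading habits. The second is timeliness: an event that is not recognized as an SAE or UADE has no 24-hour form, no required notice to the medical monitor and no prompt for a causality assessment.

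The primary endpoint, CGM time in range, is not affected.

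**Working it through.** The protocol states no figure on this point, so there is nothing to reproduce. The check sets the definitions side by side and then follows typical events through them.

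**Who each definition names (section 8.1.1)**

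| Text | Person named | Reaches a live-born infant? |
|---|---|---|
| Adverse event | Study participant | Not expressly; the infant is nowhere made a participant |
| SAE: death | Mother or fetus | Not expressly |
| SAE: medical judgment | Participant or fetus, as an example | Not expressly |
| SAE: life-threatening, hospitalization, disability | None | On a broad reading |
| SAE: congenital anomaly | None | Yes, an offspring outcome |
| UADE | None for death associated with a device | On a broad reading, and only if device-associated |

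**Typical events traced through the text**

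- Stillbirth: an SAE under the death criterion, without interpretation.
- Birth defect: an SAE, without interpretation.
- Death of a live-born infant, for example on day 3: not under the death criterion as worded. It is an SAE only if the illness behind it is classed as life-threatening or as a hospitalization and those criteria are taken to include the infant, or if the investigator's medical judgment is extended to the infant.
- NICU admission or neonatal seizure: an SAE only on the same broad reading.
- Neonatal hypoglycemia: section 8.1.2 keeps hypoglycemia off the adverse-event form unless it is severe or device-associated. Section 8.1.2.1 describes severe hypoglycemia in terms that fit an older patient, such as being disoriented or unable to speak for oneself. A site could take this as a reason not to report.

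**Follow-up**

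- Section 6.3, item 5(g) is the only planned post-delivery contact. It falls before hospital discharge; whose discharge is not said. Its stated purpose is the mother's return to her own devices.
- The schedule of assessments in section 6.3 has no post-delivery column.
- Sections 8.1.5 and 8.1.6 follow adverse events to their outcome, but this helps only once an event has been recognized as one.

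A neonatal death after the contact, or the final outcome of a NICU stay still in progress at the contact, therefore has no planned point of capture unless the event has already been reported.

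**Scale**

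Inputs: at most 21 women (section 6.3); NICU admission in 69% and 75% of cases in the two cited trials (Table 4), each with 16 women (section 2.2), which corresponds to 11/16 and 12/16.

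- 21 × 0.69 = 14.5
- 21 × 0.75 = 15.8

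This is an upper bound. It assumes that all 21 women take up the optional extension and stay in it to delivery, and that rates from two small trials carry over.

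**The case against.** The strongest reply is that this is ambiguity, not exclusion. The SAE definition opens without limiting itself to a participant. Its criteria are alternatives, and several name no person. It already reaches the offspring through fetal death and birth defects, the judgment wording is only an example, and section 7.3.1.5 speaks of a newborn fetus, so the protocol does not use fetus strictly. All of this stands. A reader might infer that a neonatal death or NICU stay can trigger no report at all; the documents do not support that. What remains is that death, the gravest event, has its own criterion with named persons, and the infant is not among them.

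A reader might also infer that neonatal outcomes are closed at the mother's discharge and so are biased toward good results. Section 6.3 does not say this. The timing belongs to the contact, the recording sentence has no cut-off, and reported events are followed to outcome. Nor does the protocol give NICU lengths of stay, so it cannot be said how many infants would still be inpatients.

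A third tempting reading is that a stillbirth reaches the DSMB at once and a neonatal death does not. Section 8.5 limits immediate notice of SAEs to device-related ones, so an unrelated stillbirth would not trigger it either. The DSMB and the medical monitor also review compiled safety data periodically, though whether that includes neonatal outcomes is not stated.

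Finally, a reader might subtract stillbirth from perinatal mortality in Table 2 to obtain a neonatal death rate. Three rows give positive values (UK 3.17 − 2.6 = 0.57%; Netherlands 2.8 − 1.86 = 0.94%; Denmark 3.1 − 2.1 = 1.0%). The other two are negative (Sweden 0.02 − 1.5 = −1.48%; England/Wales 0.81 − 1.07 = −0.26%). The columns are not comparable, and no probability of a neonatal death in this trial should be built on them.

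**Conclusion.** The point holds as a gap in wording and follow-up. A live-born infant's death is not expressly an SAE. NICU admission and neonatal seizure qualify only on a broad reading, so 24-hour recording and notice to the medical monitor rest on each site's interpretation. The single planned post-delivery contact precedes hospital discharge, and no end date is set for neonatal outcomes.

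The reach could be wide in a study of this size: up to about 14 to 16 NICU admissions, on the assumptions that every woman continues to delivery and that the Table 4 rates apply. No reliable figure for neonatal death follows from the documents, and the conclusion does not need one. It rests on the text of sections 8.1.1, 8.3, 8.4.2 and 6.3. The separate DSMB charter is not at hand and might address part of it.

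This should be corrected by amendment, as it concerns safety capture for a harm that the protocol itself names.

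**What to change.** In section 8.1.1, change the persons named in the death criterion to *mother, fetus or newborn* and those in the judgment example to *participant, fetus or newborn*. Add a sentence stating that SAE and UADE reporting covers the newborn up to a stated date; the sponsor should choose and justify that date.

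In section 6.3, item 5(g), state the date to which neonatal outcomes are recorded, and provide for one phone or chart check if the infant is still in hospital at the contact.

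The cost is a wording amendment, consent wording for access to infant records, a few more SAE forms and at most one brief check per delivery. These changes would not by themselves send a neonatal death judged unrelated to the device to the DSMB at once; if that is wanted, section 8.5 or the charter must say so.

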8.1.2 Reportable Adverse Events

For this protocol, a reportable adverse event includes any untoward medical occurrence that meets one of the following criteria:

1. A serious adverse event
2. An Adverse Device Effect as defined in section 8.1.1, unless excluded from reporting in section 8.2
3. An Adverse Event occurring in association with a study procedure
4. Hypoglycemia meeting the definition of severe hypoglycemia as defined below
5. Diabetic ketoacidosis (DKA) as defined below or in the absence of DKA, a hyperglycemic or ketosis event meeting the criteria defined below

Hypoglycemia and hyperglycemia not meeting the criteria below will not be recorded as adverse events unless associated with an Adverse Device Effect. Skin reactions from sensor placement are only reportable if severe and/or required treatment.

